APPENDIX 1: CODE LISTS

Code	Code Type	Description
518.81	ICD-9 Dx	Acute respiratory failure
518.82	ICD-9 Dx	Other pulmonary insufficiency, not elsewhere classified
518.84	ICD-9 Dx	Acute and chronic respiratory failure
799.1	ICD-9 Dx	Respiratory arrest
		Acute respiratory failure, unspecified whether with hypoxia or
J9600	ICD-10 Dx	hypercapnia
J9601	ICD-10 Dx	Acute respiratory failure with hypoxia
J9602	ICD-10 Dx	Acute respiratory failure with hypercapnia
J80	ICD-10 Dx	Acute respiratory distress syndrome
		Acute and chronic respiratory failure, unspecified whether with
J9620	ICD-10 Dx	hypoxia or hypercapnia
J9621	ICD-10 Dx	Acute and chronic respiratory failure with hypoxia
J9622	ICD-10 Dx	Acute and chronic respiratory failure with hypercapnia
R092	ICD-10 Dx	Respiratory arrest

APPENDIX 2: COPD-RELATED RESPIRATORY MEDICATIONS AND CLASSES

Drug Class	Subclass	Medication
Maintenance		aclidinium
medications	Inhaled long-acting anti-	glycopyrrolate
	muscarinic	revefenacin
	agents (LAMA)	tiotropium
		umeclidinium
		arformoterol
	Long-acting β-agonists (LABA)	formoterol
		indacaterol
		olodaterol
		salmeterol
		beclomethasone
		budesonide (both inhaler and nebulizer)
	Inhaled corticosteroids (ICS)	ciclensonide
		flunisolide
		fluticasone
		mometasone
		triamcinolone

Boehringer Ingelheim Non-Interventional Study (NIS) Protocol BI Study Number 1237-0121

c38026921-01

Proprietary confidential information © 2022 Boehringer Ingelheim International GmbH or one or more of its affiliated companies

Drug Class	Subclass	Medication	
		aclidinium/formoterol	
	Inholod I AMA/I ADA	glycopyrrolate/formoterol	
	innaled LAMA/LABA	indacaterol/glycopyrrolate	
	combination	tiotropium/olodaterol	
		umeclidinium/vilanterol	
		budesonide/formoterol	
	Inhaled ICS/LABA	fluticasone/salmeterol	
	combination	fluticasone/vilanterol	
		mometasone/formoterol	
	Inholod ICS/LADA/LAMA	Budesonide/glycopyrrolate/formoterol	
	initiated ICS/LABA/LAWA	fumarate ¹	
	combination	Fluticasone/umeclidinium/vilanterol	
	Mathulyanthing	aminophylline	
	(intravenous oral)	dyphylline	
	(intravenous, orar)	theophylline	
	PDE-4 inhibitor (oral)	roflumilast	
Rescue		albuterol	
medications		bitolterol	
	Short-acting B-agonists	isoetharine	
	(SABA) (inhalation oral)	isoproterenol	
		levalbuterol	
		metaproterenol	
		pirbuterol	
	Short-acting anti-muscarinic	ipratropium	
	Agents (SAMA) (inhalation)		
	SAMA/SABA (inhalation)	ipratropium/albuterol	
		betamethasone	
		dexamethasone	
	Oral corticosteroids $(OCS)^2$	hydrocortisone	
		methylprednisolone	
		prednisolone	
		prednisone	

¹This medication was FDA approved for maintenance treatment of COPD on 24 July 2020, which is outside of the study time period, and will not be included in this study.

²Including tablets, oral solutions, elixirs, etc. Injectable corticosteroid medications will not be included.

Proprietary confidential information © 2022 Boehringer Ingelheim International GmbH or one or more of its affiliated companies

APPENDIX 3: COPD GUIDELINE-RECOMMEND ANTIBIOTIC MEDICATIONS

Drug Category	Drug Class	Medication	
COPD Guideline-		cefaclor	
recommended Antibiotics ¹		cefdinir	
		cefditoren	
		cefepime	
	Cephalosporins	cefpodoxime	
		cefprozil	
		ceftibuten	
		ceftriaxone	
		cefuroxime	
	M	azithromycin	
	Wacrondes	clarithromycin	
		amoxicillin	
	Penicillins	amoxicillin/potassium	
		piperacillin/tazobactam	
		levofloxacin	
	Quinoiones	moxifloxacin	
	Sulfonamide	sulfamethoxazole/trimethoprim	
	combinations		
	Tetracyclines	doxycycline	

¹The American Thoracic Society (2017) and Global Initiative for Chronic Obstructive Lung Disease (2020) guidelines recommend that antibiotics for acute exacerbation of chronic bronchitis be selected based on local sensitivity patterns. For more specific recommendations, The Sanford Guide to Antimicrobial Therapy (2020) was referenced.

COPD Exacerbation Definition

- **Exacerbation Hierarchy:** Exacerbation events will be classified as severe or moderate according to the highest severity contributing event.
- **Exacerbation Episodes:** Exacerbations occurring within 14 days of each other will be considered a single exacerbation episode and will be classified according to the highest severity contributing event.
- Episode Length: The start date of the exacerbation episode will be the service date of the first event (medical encounter or pharmacy fill for an OCS or antibiotic). The end date of the exacerbation episode will be defined as the last observed exacerbation event date (or discharge date if an inpatient event) + 14 days.

Proprietary confidential information © 2022 Boehringer Ingelheim International GmbH or one or more of its affiliated companies

• Single Event Episode

- In a single event episode, the exacerbation begins with the earliest occurrence of these events: COPD exacerbation defined inpatient admission, ER visit, ambulatory visit, or corticosteroid or antibiotic dispensing as defined in Section 9.3.2.1. In a single event episode, the exacerbation ends 14 days from the start of the event, hospital discharge, or following the OCS or antibiotic dispensing, whichever is later.
- *Episode Start date* = service date of a qualifying event (inpatient admission, ED visit, ambulatory visit, or OCS or antibiotic dispensing).
 - If the qualifying event is a hospitalization, the start date is the admission date.
 - If the qualifying event is an ED visit, the start date is the service date.
 - If the qualifying event is an ambulatory visit or an OCS or antibiotic dispensing, the start date is the earliest of the associated medical visit or medication dispensing date.

Episode End Date

- \circ If the qualifying event is a hospitalization: discharge date + 14 days
- \circ If the qualifying event is an ER visit: start date + 14 days
- If the qualifying event is an ambulatory visit or an OCS or antibiotic dispensing: Fthe latest of the medical visit or medication dispensing + 14 days
- If the Episode End Date is after the end of follow-up, then set an additional flag CENSORED=1.
- NOTE: Under this definition, it is possible for the runout of a medication to exceed the End Date.
- MULTIPLE EVENT EPISODES
- If another qualifying event occurs before the episode End Date, then the episode is extended. The date of the second event is used to reset the End Date per the definition above, using information from this second event. The process continues until a 14-day period with no exacerbation qualifying events occur. The End Date is set (as defined above).
- *Episode Length:* (End date Start date) + 1

Proprietary confidential information © 2022 Boehringer Ingelheim International GmbH or one or more of its affiliated companies

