9.3 VARIABLES

The definitions for exacerbations are as below.

- A severe exacerbation will be defined as follows:
 - An inpatient admission or an ER visit with a COPD diagnosis code in the primary position; or
 - An inpatient admission or an ER visit with a diagnosis code for acute respiratory failure in the primary position and a COPD diagnosis code in any position; or
 - An inpatient admission or an ER visit with a diagnosis code for acute respiratory failure in the primary position + an inpatient admission or an ER visit within ±7 days with a COPD diagnosis code in any position.
- A moderate exacerbation will be defined as follows:
 - An ambulatory (office or outpatient) visits with a COPD diagnosis code in any position + a pharmacy claim for an oral corticosteroid (OCS) prescription within ±7 days of the office/outpatient visit; or

Proprietary confidential information © 2022 Boehringer Ingelheim International GmbH or one or more of its affiliated companies

- \circ An office or outpatient visit with a COPD diagnosis code in any position + a pharmacy claim for respiratory antibiotic prescription within ±7 days of the office/outpatient visit; or
- An office or outpatient visit with a COPD diagnosis code in any position + a pharmacy claim for an OCS + a pharmacy claim for respiratory antibiotic prescription within ±7 days of the office/outpatient visit.
- Pneumonia diagnosis: Binary indicators will be created to identify patients with a diagnosis of 1) pneumonia (Appendix 1). The time to first pneumonia diagnosis, and time to first pneumonia, during follow-up will also be captured.
- Pneumonia-related hospitalization: Binary indicators will be created to identify
 patients with an acute hospitalization with diagnosis of 1) pneumonia in any
 position (Appendix 1) The time to first pneumonia-related hospitalization during
 follow-up will also be captured.
- COPD exacerbation and/or pneumonia diagnosis: Binary indicators will be created to identify patients with each of the following composite outcomes: severe COPD exacerbation or an acute hospitalization with a diagnosis of pneumonia in any position, severe COPD exacerbation or a hospitalization with a diagnosis of pneumonia in any position, any COPD exacerbation or pneumonia diagnosis in any position, and any COPD exacerbation or pneumonia diagnosis in any position. Time to event variables will be created for each composite outcome during the follow-up period.

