The following outcomes will be measured in the baseline and follow-up periods. The baseline period will include claims occurring on the index date, except for the index medication claims, which will be included in the follow-up period.

- All-cause health care resource utilization: Indicator variables and counts of physician office visits, hospital outpatient visits, ED visits, "other" (non-inpatient) visits, inpatient stays, and pharmacy claims will be created. Other medical visits are a residual category that includes, but is not limited to, services rendered at independent laboratories, assisted living facilities, and by home health providers. An indicator variable will be created to identify inpatient stays with an acute stay during the inpatient stay, the time to first inpatient stay will also be captured. The time to first inpatient stay, the time to first eD visit during follow-up will be captured.
- COPD and/or pneumonia-related health care resource utilization: This utilization will be calculated analogously to all-cause utilization, but restricted to medical claims with a diagnosis for COPD and/or pneumonia, in any position (Appendix 1) and pharmacy claims for a COPD-related treatment (Appendix 2), including COPD-guideline recommended antibiotics (Appendix 3).

- COPD-related health care resource utilization: This utilization will be calculated analogously to all-cause utilization, but restricted to medical claims with a diagnosis for COPD in any position (Appendix 1) and pharmacy claims for a COPD-related treatment (Appendix 2), including COPD-guideline recommended antibiotics (Appendix 3)
- Pneumonia-related health care resource utilization: This utilization will be calculated analogously to all-cause utilization but restricted to medical claims with a diagnosis for pneumonia in any position (Appendix 1).
- COPD or pneumonia-attributable health care resource utilization: This utilization will be calculated analogously to all-cause utilization, but restricted to medical claims with a diagnosis for COPD or pneumonia in the primary position or a diagnosis for acute respiratory failure in the primary position and a diagnosis for COPD or pneumonia in a non-primary position (Appendix 1) and pharmacy claims for a COPD-related treatment (Appendix 2), including COPD-guideline recommended antibiotics (Appendix 3)

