9.3.1 Exposures

Patients will be assigned to one of the following mutually exclusive study cohorts based on the index pharmacy claim: Stiolto Respimat or Trelegy Ellipta. Exposure measures will be based on pharmacy dispensing of the two medications under study, namely Stiolto Respimat or Trelegy Ellipta, over a follow-up period, beginning the index date and lasting up to one year from index date. Discontinuation for index medication will be defined as a gap in index medication of \geq 45 days (sensitivity analysis with \geq 30 days can be included) following the runout of days' supply (discontinuation date = runout prior to the gap in therapy). Switch in index medication will be defined as a pharmacy fill for \geq 30 consecutive days of a non-index maintenance medication (switch date = first date of the new treatment regimen). Switch includes any other change in use of index medication by active ingredient, inclusive of a change to a different combination therapy (ICS/LABA FDC, different LAMA/LABA or LAMA/LABA/ICS FDC) change from a FDC to a free form combination therapy with mono LAMA plus mono LABA, or mono ICS plus mono LABA, or mono LAMA plus mono LABA plus mono ICS or a change to a monotherapy.

Individuals in the study cohort will be followed from the index date until the earliest of the date of a switch in treatment, addition of an ICS for the Stiolto Respimat group, discontinuation of the index COPD maintenance treatment, the end of the study period, or the end of continuous health plan eligibility. Main analyses will be further limited to the first 12 months after index date, with sensitivity analyses considering all available data.

All patients will be required to be continuously enrolled in the health plan for a minimum of 12 months. The 12 months prior to and including the index date (index date – 364 through index date) will be used to assess baseline characteristics. The period starting the day after the index date, up to a maximum of 12 months duration (index date +1 through index date +365) will be used to assess exacerbation, pneumonia, HCRU and cost outcomes. Patients will be censored at the earliest of the following: discontinuation of the index medication (Stiolto or Trelegy), switch to a non-index medication, disenrollment from the health plan, 12-months following the index date, or the end of the study period.

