9.3.2 Outcomes

9.3.2.1 Primary Outcomes

The primary outcome event for effectiveness is time to first COPD exacerbation after cohort entry. The event is defined as follows:

- Severe exacerbation:
 - Hospitalization with a principal discharge diagnosis of COPD and/or
 - An emergency department (ED) visit with a discharge diagnosis of COPD
 - An inpatient admission or an ER visit with a diagnosis code for acute respiratory failure in the primary position and a COPD diagnosis code in any position
- Moderate exacerbation:
 - \circ An antibiotic for a respiratory condition dispensed \pm an OCS

Time to the first COPD exacerbation will be measured from index date until the occurrence of a hospitalization for COPD (severe exacerbation) or ED visit for COPD (severe exacerbation) or prescription of an antibiotic \pm an OCS on the same day (moderate exacerbation). Severe and moderate exacerbations were considered as a composite for main analyses. Sensitivity analyses will include stratification by exacerbation severity.

Exacerbations will be categorized as moderate or severe and a count of any (severe or moderate), severe, and moderate will be provided.

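### Moderate exacerbations that straddle the index date fall under two conflicting dating rules, so one that began before treatment can count as the first on-treatment event

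*Combined protocol and SAP*

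**What the plan says.** - **Outcome window (Section 9.3.1).** Outcomes are assessed in "The period starting the day after the index date, up to a maximum of 12 months duration". Section 9.3 assigns index-day claims to baseline: "The baseline period will include claims occurring on the index date, except for the index medication claims".
- **What a moderate event is (Section 9.3).** A COPD office or outpatient visit with a linked fill, for example "a pharmacy claim for an oral corticosteroid (OCS) prescription within ±7 days of the office/outpatient visit". An antibiotic fill, or both drugs, also qualifies. The link works in either order.
- **When it happens, first rule (Section 9.3.2.1).** "Time to the first COPD exacerbation will be measured from index date until the occurrence" of a COPD hospitalization, a COPD ED visit, or the prescription of an antibiotic with or without an OCS. For a moderate event the clock stops at the prescription.
- **When it happens, second rule (Appendix 3, COPD Exacerbation Definition).** For an ambulatory visit or a dispensing, "the start date is the earliest of the associated medical visit or medication dispensing date".
- **Merging (Appendix 3).** "Exacerbations occurring within 14 days of each other will be considered a single exacerbation episode", and "If another qualifying event occurs before the episode End Date, then the episode is extended".
- **Boundaries.** Appendix 3 flags an episode that runs past the end of follow-up. It has no matching rule for an episode that runs across the start.
- **Recent exacerbation (Section 9.3.3).** Exacerbation in the 30 days before cohort entry is a propensity-score covariate. It is not an exclusion.

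**The concern.** The primary endpoint is time to first exacerbation, and Sections 9.1 and 9.2.2 end follow-up at the first outcome event. How the start of follow-up is handled therefore decides which event is analysed. An exacerbation that began before the first inhaler was dispensed is not an outcome of that inhaler. Under one of the two dating rules it can still become the patient's first on-treatment event, and the patient's later experience is then not used for this endpoint.

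Matching on recent exacerbation shows that the plan expects such patients. Matching may even out how often this happens in the two cohorts, but it does not reclassify the events.

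**Working it through.** The plan gives no figure for episodes open at index, so there is nothing to reproduce. The check applies the rules literally, with index as day 0 and follow-up from day 1.

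**Step 1: which pairs straddle index.** Take a visit on day v ≤ 0 and a fill on day d ≥ 1, with d − v ≤ 7. For each d from 1 to 7, v runs from d − 7 to 0, which is 8 − d values. The sum is 7 + 6 + 5 + 4 + 3 + 2 + 1 = 28 visit-first pairs. By symmetry there are 28 fill-first pairs, so 56 in all. In each direction 7 pairs have the earlier date on day 0, so 2 × (28 − 7) = 42 pairs have an onset strictly before index, as early as day 1 − 7 = −6.

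**Step 2: date them under both rules.** The Appendix 3 End Date is the later of visit and dispensing plus 14 days.

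| Pattern | Section 9.3.2.1 | Appendix 3 onset | End Date | Agree? |
|---|---|---|---|---|
| Visit day 0, antibiotic day 3 | day 3, in window | day 0, baseline | 17 | no |
| Visit day −2, antibiotic day 4 | day 4, in window | day −2, baseline | 18 | no |
| Visit day 0, antibiotic day 7 | day 7, in window | day 0, baseline | 21 | no |
| Antibiotic day −3, visit day 2 | day −3, baseline | day −3, baseline | 16 | yes |

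The conflict lies in the 28 visit-first pairs. The 28 fill-first pairs are placed in baseline by both rules. Section 9.3.2.1 names an antibiotic with or without an OCS; a fill of OCS alone is affected in the same way if the wider definition in Section 9.3 is used with prescription timing.

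**Step 3: later contacts.** A single exacerbation dated wholly to day 0 has End Date 0 + 14 = day 14. A qualifying event on days 1 to 13 extends that baseline episode if episodes are built across index. It is a new first exacerbation if they are built from follow-up claims alone. The plan does not say which.

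**Step 4: possible size.** With 3018 matched patients per group (Section 9.5), each percentage point of carry-over is 3018 × 0.01 ≈ 30 early events per group. The effect on the hazard ratio (HR) was illustrated by simulation. All inputs are assumed: 60,000 per arm, 35% one-year risk in the reference arm, exponential on-treatment censoring with mean 200 days, a cap at 365 days, and carry-over events on days 1 to 7.

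| Carry-over, reference / other arm | Share of first events (true HR 0.85) | HR, true 0.85 | HR, true 1.00 |
|---|---|---|---|
| 0% / 0% | 0% | 0.839 | 0.999 |
| 2% / 2% | 11% | 0.849 | 0.985 |
| 5% / 5% | 25% | 0.887 | 1.004 |
| 10% / 10% | 41% | 0.901 | 0.984 |
| 5% / 3% | 21% | 0.789 | 0.910 |
| 5% / 7% | 28% | 0.980 | 1.095 |

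Simulation noise: the first row has 120,000 × 0.159 = 19,080 events, so the standard error of log HR is about 2/√19,080 = 0.0145, and about √2 × 0.0145 = 0.021 for a difference between two rows. The 2% row cannot be told from no carry-over. The shifts to 0.887 and 0.789 are ln(0.887/0.839) = 0.056 and ln(0.789/0.839) = −0.061, each about three times that noise.

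**The case against.** The best defence is a joint reading. Section 9.3.1 starts outcomes at index +1, Section 9.3 puts index-day claims in baseline, and Appendix 3 gives each paired event one onset and merges later contacts without limiting this to follow-up. Read together, a straddling event belongs to baseline and a repeat contact extends it. A false first event then needs a programmer to date by Section 9.3.2.1 or to scan follow-up claims only. In addition, any imbalance above 10% in standardized difference after matching may be adjusted for in the outcome model.

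The joint reading is coherent and may be what was meant, but it is not written down. Section 9.3.2.1 is the section that defines the primary outcome, and it times the event at the prescription. Appendix 3 refers back to it for what qualifies and does not say that its own start date replaces that timing. Balance on recent exacerbation limits unequal carry-over but leaves equal carry-over in place.

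Two further points stand. A hospitalization is dated at admission, so a pre-index admission alone is never moved into follow-up; exposure is mainly through moderate events and merged episodes. And merging across index has a side effect: since an episode takes its highest severity, an admission on day 5 could vanish into a baseline moderate episode, or raise the baseline severity used for matching. The fix has to deal with this.

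**Conclusion.** The point holds as a conflict in the primary-endpoint rules. For visit-first pairs that straddle index, Section 9.3.2.1 with Section 9.3.1 permits a first on-treatment event where Appendix 3 places the onset at or before index, and nothing in the plan settles it. Exacerbations that began before treatment can therefore enter the time-to-first analysis.

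A reader might infer more than the documents support:

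- *That contamination is certain.* It depends on which rule is programmed.
- *That every straddling pair is in conflict.* Only the visit-first half is.
- *That the HR must be diluted toward 1.* That applies to equal carry-over when a true difference exists; unequal carry-over moved the simulated HR both ways.
- *That events in the first two weeks cannot reflect treatment.* The documents give no basis for this, and the argument does not need it.
- *That affected patients leave the analysis.* They stay in and contribute an event.

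The size is unknown. The documents give neither the share of patients with an episode open at index nor an expected event rate, and the simulated figures rest wholly on the stated assumptions.

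**What to change.** 1. Reconcile Section 9.3.2.1 with Appendix 3, so that one rule dates a moderate event.
2. Build episodes over baseline and follow-up claims together, and count as the first outcome only an episode with onset at index +1 or later.
3. Fix the baseline exacerbation history and severity used for matching and stratification from claims up to index only.
4. State how a new hospitalization or ED visit after index, inside an episode open at index, is treated; for example, count it as an outcome in one analysis and not in the other.
5. Add a sensitivity analysis that excludes patients with an episode open at index, or starts their risk time after that episode's End Date. A fixed start at index +15 would not do: a visit on day 0 with a fill on day 7 stays open to day 21, and an inpatient episode runs to discharge plus 14 days.

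The cost is a few written rules, a change in programming order and one added analysis, with slightly fewer early events. No new data are needed.

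### Appendix 3's episode-building rule conflicts with the protocol's own 14-day rule: an event on day 14 opens a second episode, and a nested shorter event can, read literally, move the End Date earlier

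*Combined protocol and SAP*

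**What the plan says.** The general rule in Appendix 3 (COPD Exacerbation Definition) is that "Exacerbations occurring within 14 days of each other will be considered a single exacerbation episode". Sections 9.1 and 9.2.2 give the same 14-day rule.

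Appendix 3 then sets the End Date by type of event:
- hospital stay: "If the qualifying event is a hospitalization: discharge date + 14 days"
- ED visit: "If the qualifying event is an ER visit: start date + 14 days"
- ambulatory visit or dispensing: the "latest of the medical visit or medication dispensing + 14 days"

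For episodes with several events it says: "If another qualifying event occurs before the episode End Date, then the episode is extended". It continues: "The date of the second event is used to reset the End Date per the definition above, using information from this second event". The stopping condition is: "The process continues until a 14-day period with no exacerbation qualifying events occur". Episode length is End Date minus start date, plus 1.

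Section 9.3.2.1 states that "a count of any (severe or moderate), severe, and moderate will be provided". These counts serve the third primary objective in Section 8, the comparison of COPD exacerbations after initiation.

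**The concern.** The operational rule should reproduce the 14-day rule, and in two places it does not.

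1. **Day-14 boundary (main fault).** The End Date is the event's last date plus 14, and only events before it are merged. A contact on day 14 is therefore counted as a new exacerbation.
2. **Reset of the End Date (secondary fault).** The new End Date comes from the newest event alone. If that event ends earlier than the one already in the episode, the End Date moves back, although the text describes an extension.

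Both faults split one episode into two, so both push the counts of any, severe or moderate exacerbations upward. If the same episode rule is applied at baseline, the prior-exacerbation covariate used in matching (0, 1, ≥2; Section 9.3.3) is exposed too. So, possibly, are the Low/High history strata in Section 9.7.1, where one moderate event counted as two could move a patient from Low to High.

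**Working it through.** The plan gives no figure to reproduce. The check sets the passages side by side and applies the rule to dated events.

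**Day 14.** Take ED visits on days 0 and 14. The first gives End Date 0 + 14 = 14. Day 14 is not before day 14, so a second episode opens and runs to 14 + 14 = 28. Three statements point the other way:
- The general rule makes events within 14 days one episode.
- The stopping condition needs 14 event-free days. Days 1 to 13 are only 13. With the second event on day 15, days 1 to 14 make 14, so the stopping condition agrees with merging day 14 and separating day 15.
- The first episode's length is (14 − 0) + 1 = 15 days, that is, days 0 to 14. Both episodes then contain day 14.

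**Reset.** Take a stay from day 0 to day 20, with End Date 20 + 14 = 34. An ED visit on day 5 resets it to 5 + 14 = 19, one day before discharge. An ED visit on day 25, five days after discharge, then opens a second episode. Without the day-5 visit, day 25 is before day 34 and merges, so adding an event inside the stay raises the count.

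The same happens with a visit on day 0 and its fill on day 7, a span that Section 9.3 allows (±7 days). The End Date is 7 + 14 = 21. An ED visit on day 3 resets it to 17, and an ED visit on day 18, 11 days after the fill, becomes a second episode.

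Episode counts under the rule as written and under each change, with events sorted by start date:

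| Events (days) | As written | On-or-before only | Later-of only | Both |
|---|---|---|---|---|
| ED 0, ED 13 | 1 | 1 | 1 | 1 |
| ED 0, ED 14 | 2 | 1 | 2 | 1 |
| ED 0, ED 15 | 2 | 2 | 2 | 2 |
| Stay 0–5, ED 19 | 2 | 1 | 2 | 1 |
| Stay 0–20, ED 5 | 1 | 1 | 1 | 1 |
| Stay 0–20, ED 25 | 1 | 1 | 1 | 1 |
| Stay 0–20, ED 5, ED 25 | 2 | 2 | 1 | 1 |
| Visit 0/fill 7, ED 3, ED 18 | 2 | 2 | 1 | 1 |
| Stay 0–10, visit/fill 2, visit/fill 20 | 2 | 2 | 1 | 1 |

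**Same-date events.** Take a stay from day 0 to day 10, an ED claim on day 0 and a readmission on day 20. If the ED claim is processed second, the End Date falls from 24 to 14 and the count is 2. If it is processed first, the End Date is 24 and the count is 1. The text gives no order for events on the same date.

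**Size.** The documents give no contact rates, so these figures are illustrations built on assumptions.
- *First set:* 0.8, 1.5 or 3 index events a year; after each event, a 40% chance of a further one 1 to 30 days later; 15% of events are stays of 2 to 8 days. Against the rule with both changes, counts as written are 2.2%, 2.3% and 3.0% higher. The boundary alone accounts for 2.1%, 2.2% and 2.8%, and the reset alone for 0.1%, 0.1% and 0.2%. Follow-on events start at least one day later, so same-date ED claims within a cluster are left out.
- *Second set:* 20% of episodes hospitalised, mean stay 5 days, follow-on contact 0.5–1.5% per day, 0–4% of episodes with a contact on day 14, and 35–70% of stays with a same-day ED claim processed second. Counts are 0.6–4.7% higher overall, and the boundary alone gives 0.4–4.1%. The reset alone gives 0.8–5.8% of hospitalised episodes; at a 20% share that is 0.2 × 0.8% to 0.2 × 5.8%, about 0.2–1.2% of all episodes.

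**The case against.** The best defence concerns the reset. The text says the episode is extended, and an extension cannot shorten it. Appendix 3 also gives a general End Date of 14 days after the last observed event, or after discharge for an inpatient event, which a sensible programmer would use to avoid closing an episode before discharge. The stopping condition also works against splitting in the visit-and-fill example. This stands in part: the reset is a defect of the literal text that a careful reader may resolve. But the text does not require it. It does not settle whether the last event is the latest to start or the latest to end, and the single-event rule does say to take the later date where this one does not.

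For day 14, one could read the 14-day rule as fewer than 14 days. The stopping condition and the length formula do not fit that reading.

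Several stronger inferences are tempting but unsupported:
- *Nesting by itself double-counts.* It does not. With no further event the count stays at 1, and only the End Date, the episode length and the censoring flag change.
- *Baseline history is certainly distorted.* Section 9.3.3 does not cite the Appendix 3 algorithm, and Section 9.7.1 words its strata as events. One inpatient event already places a patient in the High stratum, so a split hospital episode cannot move anyone.
- *The treatment comparison is biased.* The rule is the same in both arms, and nothing shows different contact patterns. Sections 9.7 and 9.7.1 name no count model or rate ratio.
- *The percentages are estimates for this study.* They follow their inputs: the 4.1% upper end for the boundary nearly equals the assumed 4% of contacts on day 14.

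**Conclusion.** The rule is wrong as written, with minor severity. The day-14 boundary contradicts the 14-day rule in Sections 9.1 and 9.2.2 and in Appendix 3 itself, and it is the main fault. The reset is a secondary, literal-reading fault. It raises the count only when a further event falls on or after the shortened End Date and on or before the original one, or, for same-date events, according to sort order.

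The established effect is on exacerbation counts. Any effect on the matching covariate and, for moderate events, the strata depends on whether the same episode rule is used at baseline. A reader might infer that the primary time-to-event result is at risk. It is not, because the date of the first event does not depend on how later events are merged. The size is probably a few percent of counts or less, resting wholly on assumed contact rates, and no between-arm bias is shown.

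**What to change.** In the multiple-event part of Appendix 3, replace the merge and reset sentences with this rule: a qualifying event that starts on or before the current End Date joins the episode, and the End Date becomes the later of the current one and the one computed from the new event. A new episode then starts no earlier than the day after the End Date. State that the rule applies to both baseline and follow-up.

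This brings the operational rule into line with the general 14-day rule, the stopping condition and the length formula, and it makes the result independent of the order of same-date claims. All the disputed sequences above become one episode, while events on days 0 and 15 remain two. The cost is one sentence and one line of code, with no new data. Counts become slightly lower.
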